## 1. Synopsis

- Design: Interventional, randomized, parallel-group, three-arm study conducted in maternity units.
- Arms: (A) Early one-time skin-to-skin contact; (B) Frequent skin-to-skin contact; (C) Standard care comparator.
- Primary Endpoint: Paternal-Infant Attachment Scale (PIAS) total score at approximately 3 months postpartum (points; higher scores indicate stronger bonding).
- Secondary Endpoints: PIAS subscale scores; frequency (days/week) and daily minutes of skin-to-skin contact; selected caregiving behaviors.
- Population: Adult fathers of healthy term singleton newborns.
- Setting: University and state hospital obstetrics units in Türkiye.
- Duration per participant: Baseline assessment soon after birth and a follow-up assessment around 3 months postpartum.

## 2. Background and Rationale

Skin-to-skin contact between caregivers and newborns is a simple, low-cost practice that may foster early bonding. Experimental evidence focusing on fathers is comparatively limited in Türkiye. This study evaluates whether structured father-infant skin-to-skin contact schedules enhance bonding versus standard care.

## 3. Objectives

Primary Objective. To determine whether father-infant skin-to-skin contact improves paternal-infant bonding compared with standard care.

Secondary Objectives. To compare subscale scores of bonding, describe skin-to-skin frequency and duration, and explore associations with selected caregiving behaviors and sociodemographic factors.

## 4. Endpoints

Primary Endpoint. PIAS total score at 3 months postpartum.

Secondary Endpoints. PIAS subscale scores; frequency of skin-to-skin (days/week); daily minutes of skin-to-skin; indicators of paternal involvement.

## 5. Trial Design

Randomized, parallel assignment with three arms and approximately equal allocation. The early one-time arm includes a single skin-to-skin session soon after birth. The frequent arm includes repeated sessions (e.g., at least 15 minutes per session on most days). The comparator arm receives routine postnatal care without a structured schedule.

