## 6. Study Setting

The study is conducted in obstetrics units of a university research hospital and a state hospital in Türkiye.

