## 8. Interventions

**Early One-Time Skin-to-Skin:** A single supervised session of skin-to-skin contact shortly after delivery, following unit procedures.

**Frequent Skin-to-Skin:** Repeated sessions encouraged at home and/or during postnatal stays (e.g., on most days of the week), each lasting approximately 15 minutes, as feasible for the family.

**Standard Care:** Routine postnatal care without a structured skin-to-skin schedule; families may practice contact ad libitum per usual care.

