# Statistical Analysis Plan (SAP)

This SAP outlines analyses for the primary and secondary endpoints, populations for analysis, handling of missing data, and statistical thresholds. Analyses use a two-sided alpha of 0.05 unless otherwise noted.

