## 15. Primary Endpoint Analysis

Group comparisons of PIAS total scores at 3 months postpartum will be performed using a nonparametric omnibus test (e.g., Kruskal-Wallis). If the omnibus test is significant, post-hoc pairwise comparisons will be conducted with appropriate adjustments for multiplicity.

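### Hospital is not named in the allocation, and the stated primary rank test ignores it; this costs precision and leaves chance imbalance uncorrected, without making the test invalid.

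*Combined protocol and SAP*

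**What the plan says.** - **Sites.** Section 6 names two unlike sites: "The study is conducted in obstetrics units of a university research hospital and a state hospital in Türkiye".
- **Allocation.** Section 5 says "Randomized, parallel assignment with three arms and approximately equal allocation". It gives no method of sequence generation, no blocking or stratification, and no unit of randomisation.
- **Arms tied to local practice.** Section 8 defines the comparator as "Routine postnatal care without a structured skin-to-skin schedule; families may practice contact ad libitum per usual care" and the early arm as "A single supervised session of skin-to-skin contact shortly after delivery, following unit procedures".
- **Primary analysis.** The endpoint is "PIAS total score at 3 months postpartum" (Section 4). Section 15 says: "Group comparisons of PIAS total scores at 3 months postpartum will be performed using a nonparametric omnibus test (e.g., Kruskal-Wallis"), followed by adjusted pairwise tests if the omnibus test is significant. The SAP's opening paragraph sets the level: "Analyses use a two-sided alpha of 0.05 unless otherwise noted".
- **Covariates.** Section 17 allows optional adjusted models. Its examples are education, the partner's employment and caregiving involvement. Sections 13 to 19 do not mention hospital.

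**The concern.** The primary objective is a contrast with standard care, and standard care here is whatever each hospital routinely does. If usual father-infant contact, or the general level of PIAS scores, differs between the hospitals, the level seen in each arm depends partly on its hospital mix. Nothing stated in the plan balances that mix or takes it out of the primary comparison.

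Two things are at stake. In the one trial that is run, an arm may by chance hold more fathers from one hospital, and the unadjusted comparison cannot separate that from the intervention. Over repeated trials, the same variation appears as noise and lowers power. The enrolling hospital is known for every father, so the plan leaves useful information unused.

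**Working it through.** The documents give no sample size, SD, effect size, hospital split or hospital difference, so there is no stated figure to reproduce. From the documents come three arms of roughly equal size, two hospitals, two-sided alpha 0.05 and an unstratified rank test. The assumptions are individual randomisation, a 50:50 hospital split and normal scores. Write *h* for the hospital difference in PIAS, in within-hospital SDs, and *n* for fathers per arm.

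**1. Chance imbalance if allocation ignores hospital.** Each arm's count from one hospital is binomial(*n*, 0.5). Exact probabilities of a gap of 20 percentage points or more in hospital share:

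| *n* per arm | one intervention arm vs standard care | any pair of the three arms |
|---|---|---|
| 30 | 15.5% | 32.9% |
| 40 | 9.3% | 21.3% |
| 60 | 3.5% | 8.9% |

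A 20-point gap shifts the arm difference by 0.2 × *h*: 0.10 SD at *h* = 0.5 and 0.20 SD at *h* = 1.

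**2. Precision lost.** The variance of the difference between two arms is 2/*n* from within-hospital variation, plus *h*² × (2 × 0.25/*n*) from the varying hospital share. The total is (2/*n*)(1 + 0.25*h*²), so relative efficiency is 1/(1 + 0.25*h*²).

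- *h* = 0.3: 1/1.0225 = 0.978, a loss of about 2%
- *h* = 0.5: 1/1.0625 = 0.941, about 6%
- *h* = 0.8: 1/1.16 = 0.862, about 14%

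Steps 1 and 2 describe one cost, not two: the extra variance is the chance imbalance, averaged over trials.

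In numbers of fathers, a two-arm contrast with an assumed 0.5 SD effect and 80% power needs 63 per arm with no hospital difference. If hospital is ignored it needs 64, 67, 73 or 79 per arm at *h* = 0.25, 0.5, 0.8 or 1.0.

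**3. If allocation is stratified but the test is not.** Balance removes the hospital term from the true variance, but the test still counts it as error. The statistic shrinks by the factor 1/(1 + 0.25*h*²). The tail of a chi-square on 2 df is exp(−x/2), so the approximate type I error is 0.05 raised to the power (1 + 0.25*h*²). At *h* = 0.5 this is 0.05^1.0625 = 4.1%. At *h* = 1 it is 0.05^1.25 = 2.4%.

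**4. Simulation of the three-arm test.** 64 per arm and 3,000 trials per setting, with assumed arm shifts of 0, 0.25 and 0.5 SD for power. KW is Kruskal-Wallis ignoring hospital; SR is a hospital-stratified rank test of van Elteren type.

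| *h* | Allocation | Type I, KW | Type I, SR | Power, KW | Power, SR |
|---|---|---|---|---|---|
| 0 | ignores hospital | 4.5% | 4.4% | 68.5% | 67.7% |
| 0 | stratified | 5.4% | 5.3% | 67.5% | 67.0% |
| 0.5 | ignores hospital | 5.4% | 5.5% | 66.3% | 67.7% |
| 0.5 | stratified | 4.0% | 4.8% | 66.5% | 69.3% |
| 1.0 | ignores hospital | 4.4% | 4.7% | 59.4% | 69.1% |
| 1.0 | stratified | 2.4% | 4.8% | 56.5% | 68.9% |

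The simulation standard error is about √(0.68 × 0.32/3000) = 0.9 points for power and √(0.05 × 0.95/3000) = 0.4 points for type I error. Differences of a point or so in power are therefore within noise.

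**The case against.** The strongest reply is that validity is not at stake. A reader might infer that hospital differences bias the comparison with standard care or produce false positives. The documents do not support that: under individual randomisation, chance imbalance is already covered by the 5% level, and the simulated type I error of the unstratified test stays near or below 5%. This part of the reply stands in full.

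A reader might also infer that allocation is known to be unstratified, or that arms were assigned by hospital and so confounded with it. Section 5 supports neither. It is silent on method and on the unit of randomisation, and silence does not rule stratification out. Likewise, the test and the covariates are given as examples, so hospital could still enter an optional adjusted model. But that model is not the primary analysis. If allocation is stratified, the stated test becomes conservative, so the analysis point holds either way.

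The size may well be small. Both sites enrol only cohabiting first-time fathers of healthy term singletons, which may narrow the hospital difference, and nothing in the documents suggests one near 1 SD. This also stands.

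Finally, if usual care differs between the hospitals, the treatment contrast itself may differ. Stratification does not remove that. Routine care is a legitimate comparator, but the objection shows that results by hospital are needed as well.

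**Conclusion.** The point holds as a matter of precision and of chance imbalance in the realised trial. It is not a claim of bias. Two unlike hospitals enrol, stratified allocation is not stated, and the named primary test ignores hospital.

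The cost is slight for hospital differences up to about 0.5 SD: roughly 6% of the effective sample, or 67 rather than 63 fathers per arm in the illustration. It becomes material near 1 SD, where simulated power was 59% against 69% with allocation ignoring hospital, and about 57% against 69% with stratified allocation. Chance imbalance matters most if the arms are small. All these sizes rest on assumed inputs, so the effect in this trial cannot be determined from the documents. The case for the change rests on its very low cost.

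**What to change.** **Section 15.** Replace the plain Kruskal-Wallis test with its hospital-stratified form: the Cochran-Mantel-Haenszel row-mean-scores test on within-hospital ranks, with van Elteren tests for the pairs. An equivalent analysis with hospital as a fixed factor would also serve. Choose one and record it before any comparison between arms is seen.

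**Section 5.** State how the allocation sequence was generated and whether it was stratified by hospital. If enrolment is not complete, randomise in blocks within each hospital. If it is complete, make only the analysis change. Stratified allocation alone is not enough, since the unstratified test then becomes conservative.

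**Reporting.** Show PIAS results by arm within each hospital, descriptively. The contact frequency and minutes already collected under Section 9 can be tabulated the same way, to show how far usual care differed.

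**Cost.** One or two sentences in the plan and, if enrolment is open, two allocation lists. No new data are needed. If the hospitals are alike, essentially no power is lost (68.5% against 67.7% in the simulation, within its error).

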## 6. Study Setting

The study is conducted in obstetrics units of a university research hospital and a state hospital in Türkiye.

## 7. Eligibility Criteria

### Inclusion Criteria:

- Fathers aged 18 years or older.
- First-time fathers residing with the mother and infant.
- Able to provide skin-to-skin contact (e.g., sessions of approximately 15 minutes) within a defined post-birth window.
- At least primary school education.
- Infant: healthy, term ( $\approx$ 38-42 weeks' gestation), singleton, with birth weight within an acceptable range per protocol.

### Exclusion Criteria:

- Significant communication barriers or conditions limiting informed consent.
- Infants requiring special care or with major congenital anomalies/serious illness.
- Sustained separation from the infant (e.g., prolonged hospitalization or travel) that precludes scheduled follow-up.

## 8. Interventions

**Early One-Time Skin-to-Skin:** A single supervised session of skin-to-skin contact shortly after delivery, following unit procedures.

**Frequent Skin-to-Skin:** Repeated sessions encouraged at home and/or during postnatal stays (e.g., on most days of the week), each lasting approximately 15 minutes, as feasible for the family.

**Standard Care:** Routine postnatal care without a structured skin-to-skin schedule; families may practice contact ad libitum per usual care.

## 9. Assessments and Schedule

Assessments include a baseline questionnaire administered soon after birth and a follow-up evaluation at approximately 3 months postpartum, which includes the PIAS. Additional questionnaires capture frequency (days/week) and daily minutes of skin-to-skin, and caregiving behaviors. All assessments are performed with standardized instructions.

## 10. Safety Considerations

This is a minimal-risk behavioral study. No investigational drugs or devices are used. Adverse events are not anticipated beyond transient discomfort from holding position. Any unexpected concerns reported by participants will be documented and managed according to institutional policies.

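### Section 10's recording rule leaves out the one harm the protocol anticipates and gives infant and staff-observed events no route except the father's report, and no listed assessment or SAP table covers harm

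*Combined protocol and SAP*

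**What the plan says.** Section 10 (Safety Considerations) is the only section that deals with harm. It describes the study as minimal-risk and states what is expected: "Adverse events are not anticipated beyond transient discomfort from holding position." The recording rule follows: "Any unexpected concerns reported by participants will be documented and managed according to institutional policies."

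Section 9 (Assessments and Schedule) lists what is collected: "Assessments include a baseline questionnaire administered soon after birth and a follow-up evaluation at approximately 3 months postpartum, which includes the PIAS." It adds: "Additional questionnaires capture frequency (days/week) and daily minutes of skin-to-skin, and caregiving behaviors."

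Section 8 (Interventions) gives the three arms different conditions:

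- Early one-time arm: "A single supervised session of skin-to-skin contact shortly after delivery, following unit procedures."
- Frequent arm: "Repeated sessions encouraged at home and/or during postnatal stays."
- Standard care: "Routine postnatal care without a structured skin-to-skin schedule; families may practice contact ad libitum per usual care."

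The SAP introduction sets its scope: "This SAP outlines analyses for the primary and secondary endpoints, populations for analysis, handling of missing data, and statistical thresholds." Section 4 (Endpoints) has no safety or tolerability endpoint.

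**The concern.** The rule in Section 10 has two conditions: the concern must be unexpected, and a participant must report it. The first excludes the only harm that the protocol foresees. The second makes the father the sole stated source, although the infant is the other party to every session and one arm's session is supervised.

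What is at stake is the tolerability record. If the trial favours one of the contact schedules, readers will want to know how often fathers found holding uncomfortable and whether infant problems were noted. A plan followed as written commits to no count of the first and to only an unprompted, father-reported account of the second. A short or empty list of concerns could not then be read as support for the expectation in Section 10.

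**Working it through.** No arithmetic applies. The documents give no sample size, event rate or safety threshold, so the check is to apply the text to each kind of event and then look for another section that fills the gap.

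**Step 1. Who the participants are.** Section 1 defines the population as adult fathers, and Section 11 takes consent from the participating fathers. A report by a participant is therefore a report by a father.

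**Step 2. The Section 10 rule applied to each kind of event.**

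| Event | Unexpected under Section 10? | Stated route into the record |
|---|---|---|
| Holding discomfort, reported by the father | No, it is the named expectation | None |
| Any other problem of the father's, reported by him | Yes | Documented |
| Infant problem, reported by the father | Yes | Documented |
| Infant problem, not reported by the father | Yes | None |
| Event seen by staff at the early session, not reported by the father | Yes, unless it is holding discomfort | None |

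The word unexpected thus removes one minor event. The reporting condition leaves out whatever the father does not mention.

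**Step 3. Is anyone asked?** Section 9 lists a baseline questionnaire, the attachment scale at about 3 months, and questionnaires on days per week, daily minutes and caregiving. None is said to ask about discomfort or infant health. That reports would be spontaneous is an inference from this, since Section 10 itself says only that they are reported.

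**Step 4. Is anything analysed?** Sections 1 and 4 list no safety outcome. Section 13 defines an intent-to-treat and a per-protocol population but no safety population. Sections 15 to 19 cover the primary and secondary endpoints, covariates, missing data and multiplicity. No harm table or summary by arm appears. Section 14 does give a usable format for categorical items, counts and percentages.

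**Step 5. Would unprompted counts be comparable across arms?** All three arms share the same rule and the same planned assessments. Section 8, however, gives the early arm one supervised session. It gives the frequent arm repeated sessions that may be at home, with no supervision stated, and standard care no structured session. Without a common question, a difference in counts could arise from a difference in harm, in the number of occasions to notice something, or in who was present. The documents give no reporting proportion or delivered number of sessions from which to separate these.

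**The case against.** The strongest reply is that the gap is small and the trial never set out to compare harms. There is no safety objective, the infants are healthy and at term, and an ethics committee approved the study. Every event other than holding discomfort is unexpected by the protocol's own wording, so it is documented once a father reports it. Section 10 does not forbid recording discomfort either. Section 9 says that assessments include the listed items, and it does not itemise the baseline questionnaire, so an unlisted harm question is possible. All of this stands, and it limits the point to a minor one. It does not supply a commitment to record the named harm, to ask about harm, or to summarise it.

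Four stronger readings are tempting, and the documents do not support them:

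- *The father decides what counts as unexpected.* Section 10 gives him no such role. Its own preceding sentence sets the expectation.
- *The trial will show almost no harms whatever happens.* An unexpected event that a father reports would be documented, and no reporting proportion is given.
- *The most exposed arm is the least observed.* Section 8 does not say who supervises the early session, how the frequent sessions divide between home and hospital, or for how long they continue.
- *The 3-month assessment is the only later data collection.* Section 9 ties only the attachment scale to that time. The additional questionnaires are undated.

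**Conclusion.** The point holds as a minor, inexpensive improvement. As written, the one anticipated harm falls outside the recording rule, infant and staff-observed events have no stated route other than the father's report, no listed assessment asks about harm, and the SAP summarises none.

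It rests on a literal reading of Section 10 and on taking the lists in Section 9 and the SAP as the plan's actual commitments. Counts by arm of spontaneous reports could mix harm with opportunity to report. This is a methodological consequence of the differing arm conditions, and its size and direction cannot be estimated from the documents. A reader might go on to infer a bias against or in favour of a particular arm, but nothing in the text fixes its sign. The primary analysis in Section 15 is not affected.

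**What to change.** Three short edits:

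1. **Section 10.** State that discomfort during holding and infant problems are documented whether or not they were expected, and whether the father reports them or staff observe them.
2. **Section 9.** Add one or two items, worded identically in all three arms, to the existing 3-month assessment: discomfort while holding the infant, and any infant problem since birth. Do not tie the wording to skin-to-skin sessions, because standard care has no scheduled ones.
3. **SAP.** Add one descriptive table of these items by assigned arm, with counts, percentages and the number of fathers answering, in the format that Section 14 already uses. List staff-observed events at the supervised session separately, since only the early arm has a session described as supervised.

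The cost is a brief amendment and a slightly longer form at an assessment already planned. The downsides are imperfect recall of minor discomfort over about 3 months and the capture of some ordinary infant illness unrelated to holding. The second should appear in all arms, and the table should be read with that in mind.

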## **11. Ethics and Oversight**

The study was reviewed and approved by an institutional ethics committee. Written informed consent is obtained from all participating fathers prior to enrollment. The protocol adheres to the principles of the Declaration of Helsinki and relevant national regulations.

## **12. Data Management and Confidentiality**

Data are recorded on de-identified forms and stored securely. Access to identifiable information is restricted to authorized personnel. Results will be disseminated in aggregate form without personal identifiers.

# Statistical Analysis Plan (SAP)

This SAP outlines analyses for the primary and secondary endpoints, populations for analysis, handling of missing data, and statistical thresholds. Analyses use a two-sided alpha of 0.05 unless otherwise noted.

## 13. Analysis Populations

Intent-to-Treat (ITT): All randomized participants with at least one post-baseline assessment. Per-Protocol (PP): Subset without major protocol deviations.

## 14. Descriptive Statistics

Continuous variables: mean, standard deviation, median, minimum, and maximum. Categorical variables: counts and percentages.

## 15. Primary Endpoint Analysis

Group comparisons of PIAS total scores at 3 months postpartum will be performed using a nonparametric omnibus test (e.g., Kruskal-Wallis). If the omnibus test is significant, post-hoc pairwise comparisons will be conducted with appropriate adjustments for multiplicity.

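### The primary objective is a comparison with standard care, but the primary test is a non-directional three-arm omnibus and no named contrast decides the claim

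*Combined protocol and SAP*

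**What the plan says.** The primary objective in Section 3 is "To determine whether father-infant skin-to-skin contact improves paternal-infant bonding compared with standard care". Section 2 frames the question the same way: "This study evaluates whether structured father-infant skin-to-skin contact schedules enhance bonding versus standard care". Both are directional, and both name standard care as the reference.

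Section 5 describes the design as "Randomized, parallel assignment with three arms and approximately equal allocation". Two of the three arms receive skin-to-skin contact: one supervised session, or repeated sessions on most days (Section 8). The third arm is defined as "Routine postnatal care without a structured skin-to-skin schedule; families may practice contact ad libitum per usual care". The primary endpoint in Section 4 is "PIAS total score at 3 months postpartum", and the opening of the SAP says "Analyses use a two-sided alpha of 0.05 unless otherwise noted".

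For the primary analysis, Section 15 states: "Group comparisons of PIAS total scores at 3 months postpartum will be performed using a nonparametric omnibus test (e.g., Kruskal-Wallis". It continues: "If the omnibus test is significant, post-hoc pairwise comparisons will be conducted with appropriate adjustments for multiplicity". Section 19 repeats that pairwise tests will be adjusted, but names neither the method nor the set of comparisons it covers. No section says which comparison decides the objective.

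**The concern.** The objective and the test ask different questions. The objective asks whether fathers with skin-to-skin contact score higher than fathers under standard care. The omnibus asks whether the three arms differ in any way, in any direction. It counts a difference between the two skin-to-skin arms as fully as a difference from standard care.

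Two consequences follow. First, a significant primary test does not say whether the objective is met. The comparisons that could say so are labelled post hoc and are not tied to the claim, so the rule for success can be settled after the results are known. Second, if all three pairs are adjusted together, the comparison outside the objective uses up part of the error budget. Under Bonferroni, each control contrast is tested at 0.05/3 = 0.0167 rather than 0.05/2 = 0.025.

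The two schedules differ widely in intensity, so a result that differs by arm is a realistic outcome, and the rule for reading it should already be written down.

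**Working it through.** **Inputs.** From the documents: three arms, about equal allocation (Section 5); two-sided alpha 0.05 (SAP opening); Kruskal-Wallis as the example omnibus, then adjusted pairs (Section 15). There is no sample size, power, effect size or SD, so there is no planned figure to reproduce. Assumed for illustration: normal scores, equal SD, 50 fathers per arm, effects in SD units relative to standard care.

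**Step 1: one constructed data set.** Take normal quantiles, 50 per arm, with early at -0.3, standard care at 0 and frequent at +0.3 SD. With N = 150 the average rank is 75.5. By symmetry the mean ranks are 75.5 - d, 75.5 and 75.5 + d, with d = 12.34.
- Omnibus: H = 12/(150 × 151) × 50 × 2 × 12.34² = 8.07 on 2 df, p = exp(-8.07/2) = 0.018.
- Standard error of a mean-rank difference (Dunn): √(150 × 151/12 × 2/50) = √75.5 = 8.69.
- Early versus frequent: z = 24.68/8.69 = 2.84, p = 0.0045; × 3 = 0.0135.
- Each arm versus standard care: z = 12.34/8.69 = 1.42, p = 0.156; × 3 = 0.47.

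The primary test is significant, early versus frequent is significant, and neither contrast named in the objective is.

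**Step 2: how often this happens.** Simulation with 2,500 to 3,000 trials per scenario: Kruskal-Wallis at 0.05 as the gate, then Mann-Whitney pairs at 0.05/3. The Monte Carlo standard error is below 1 point (for 35%: √(0.35 × 0.65/2500) = 0.0095).

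| True effect, early / frequent (SD) | Omnibus significant | Omnibus significant, no control contrast significant | Early versus frequent the only significant pair |
|---|---|---|---|
| 0 / +0.5 | 71% | 21% | 16.5% |
| -0.25 / +0.25 | 57% | 35% | 32% |
| +0.25 / +0.5 | 57% (51% with a control contrast showing benefit + 6%) | 6% | 2% |
| +0.5 / +0.5 | 70% | 4-5% | about 0% |

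In the first row, the gap between 21% and 16.5% is trials in which no adjusted pair is significant at all.

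**Step 3: sensitivity.** For the first two rows, with 30 to 80 per arm, the third column runs 14-21% and 22-41%. At 50 per arm it falls to 15% and 29% with Bonferroni over the two control pairs, and to 8% and 17% with unadjusted pairs after the gate.

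**Step 4: effect of naming the two control contrasts.** At 50 per arm, testing two contrasts instead of three gated pairs raises the chance of showing a real benefit:
- Only frequent works (+0.5 SD): from 49-51% to 54-57%.
- Both work (+0.5 SD): from 66% to 69-73%.

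The ranges cover Mann-Whitney and Dunn versions. The gain is 3 to 7 points.

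**Step 5: error rate with no effect in any arm.** The omnibus rejects in about 5% of trials. Two control contrasts at 0.025 each, without the gate, falsely declare benefit in about 2.3%.

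**The case against.** The strongest reply is that the plan does not stop at the omnibus. A significant result leads to adjusted pairwise comparisons, which with three arms would naturally include both contrasts with standard care. Sections 2 and 3 point the reader to those pairs, and no section says that a significant omnibus meets the objective. This stands, and it limits the point: the control contrasts would probably be computed and reported. What is missing is the statement that they decide the claim.

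The scenarios are also open to challenge. The two large percentages need early contact to have no effect or a negative one, and nothing in the documents suggests that it is harmful. The partial argument is that standard care allows contact at will, so it could score between the two active arms. Where both arms work, the problem is small. The percentages also move with the adjustment, as Step 3 shows. Both objections stand.

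Three stronger readings are tempting, and the documents do not support them:
- **Early versus frequent alone could carry the trial to success.** This holds only for significance in a sample. If those two arms truly differ, at least one truly differs from standard care, perhaps unfavourably. The planned pairwise step would also show where the difference lies.
- **The same data could support opposite conclusions, depending on whether the arms are pooled.** No pooled analysis appears anywhere: Sections 1, 5 and 8 keep the arms separate, and Section 2 speaks of schedules in the plural. The ambiguity that remains is whether one arm or both must beat standard care. That is not trivial: with early +0.25 and frequent +0.5 SD at 50 per arm, the either-arm rule succeeds in 51% of trials and the both-arm rule in 10%.
- **Type I error is inflated.** It is not, with no effect in any arm (Step 5).

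**Conclusion.** The concern holds in limited form. The primary test is not matched to the primary objective, and no pre-specified contrast decides the claim. That follows from the text alone and needs no assumption about sample size.

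Its practical size depends on assumptions. With normal scores, equal SD, 50 fathers per arm and Bonferroni over three pairs, a significant omnibus comes with no significant control contrast in about 21% of trials if only frequent contact works, about 35% if the arms fall either side of standard care, and about 4-6% if both work. Leaving early versus frequent in the primary family costs 3 to 7 points of power in the cases examined.

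The data remain analysable whatever is decided. What needs repair is the decision rule, and it should be repaired before the data are analysed.

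**What to change.** Add to Section 15, in substance:
- The primary objective is decided by two pre-specified contrasts on the 3-month PIAS total: frequent versus standard care, and early one-time versus standard care.
- Multiplicity is controlled over these two, for example by Holm: the smaller p-value against 0.025 and, if that passes, the larger against 0.05.
- Benefit is claimed separately for each schedule, and only when its own contrast is significant and favours skin-to-skin contact.
- Early versus frequent is a secondary comparison.
- A significant omnibus alone does not meet the objective. The section should also say whether the omnibus is kept as a gate; Holm over two contrasts does not need one.

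Whether a general claim about skin-to-skin contact requires both contrasts is for the sponsor to decide, and to state before the data are analysed.

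The cost is a few sentences of SAP text, with no new data, visits or fathers. The small downside is that early versus frequent loses its place in the primary family, and a significant omnibus alone can no longer be reported as success.
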